Data is available from 1 Phase 1b first-in-infant study (ALS-8176-503) and 1 Phase 2b study (64041575RSV2004) in hospitalized pediatric subjects with RSV infection. The clinical phase of Study ALS-8176-503 has been completed, but the database has not yet been locked.

Seventy pediatric subjects were treated in the SAD part of Study ALS-8176-503. Fifty-three subjects received single doses of ALS-008176 up to 25 mg/kg and 17 subjects received placebo. All AEs were of mild or moderate severity, except for 1 \geq Grade 3 SAE of bacterial pneumonia which was considered unrelated to the study drug.

In the MAD part of Study ALS-8176-503, 111 pediatric subjects were treated, of which 78 received multiple doses of ALS-008176 up to a 60 mg/kg LD followed by 40 mg/kg MDs twice daily, and 33 subjects received placebo twice daily. All AEs were of mild or moderate severity, except for 6 Grade \geq 3 AEs of neutropenia (N=2 Grade 3 and N=4 Grade 4), 1 Grade 3 AE of respiratory failure, and 1 Grade 3 AE of anemia. Four SAEs were reported: lymphadenitis,

neutropenia, bronchiolitis, and respiratory failure. Only the Grade 4 SAE of neutropenia (laboratory Grade 4) reported within 17 hours after the first dose of ALS-008176 (40 mg/kg LD/20 mg/kg MD twice daily) was considered possibly related to the study drug, and resulted in premature discontinuation of the study drug after the second MD. The subject experiencing a Grade 3 SAE of respiratory failure presented also a Grade 2 bacterial pneumonia, and was discontinued from the study on Day 2.

In Study 64041575RSV2004, a Grade 4 SAE of febrile neutropenia (laboratory Grade 4) that started 1 day after the last dose of study treatment was reported in a pediatric subject. The event was considered possibly related to the study drug by the investigator.

1.2. Rationale for the Study

RSV is associated with considerable morbidity and mortality, particularly at the extremes of age (ie, infants and elderly). In the United States alone, among patients >65 years of age, 177,000 hospitalizations and approximately 14,000 deaths per year are attributable to RSV infection.⁷ In other countries, the 60-day mortality rate for adults hospitalized with RSV infection has been observed to be as high as 13.8%.¹⁴ There are currently no approved treatments or vaccines to prevent RSV infection in adults. As such, there is a significant unmet medical need for an RSV therapeutic.

This study is designed to determine the antiviral activity, clinical outcomes, safety, tolerability, and PK of multiple ALS-008176 dosing regimens in a population of hospitalized adults naturally infected with RSV. The study will be performed in 2 parts. In Part 1, the PK will be characterized in the low-dose arm of 750 mg LD/250 mg MD ALS-008176. Furthermore, the safety and tolerability of this regimen will be investigated before proceeding to Part 2 of the study which will include the high-dose arm of 1,000 mg LD/500 mg MD ALS-008176. In Part 2, the dose-response relationship of the 750 mg LD/250 mg MD and the 1,000 mg LD/500 mg MD ALS-008176 dosing regimens on antiviral activity will be evaluated. The results of this study will assist in determining the design for subsequent studies in a similar RSV-infected adult population.

Note that, as per Amendment 2, the study will be performed in 2 parts. The 2 subjects (1 on ALS-008176 and 1 on placebo) that were enrolled before the study was temporarily halted, are defined as Part 0. For details, refer to Section 1.1 Background, page 42.

2. OBJECTIVES, ENDPOINTS, AND HYPOTHESIS

2.1. Objectives and Endpoints

2.1.1. Objectives

Primary Objectives

For Part 1:

The primary objective is to characterize the PK and to confirm the popPK model derived from healthy volunteers in hospitalized adults who are infected with RSV.

For Part 2:

The primary objective is to determine in hospitalized adults who are infected with RSV the dose-response relationship of multiple regimens of ALS-008176 on antiviral activity based on nasal RSV shedding using qRT-PCR assay.

Secondary Objectives

The secondary objectives for Part 1 and Part 2 are to determine in hospitalized adults who are infected with RSV:

- The safety and tolerability of ALS-008176.
- The impact of ALS-008176 on the clinical course of RSV infection including:
 - Duration of hospital stay.
 - Duration of supplemental oxygen.
 - Evolution of Activities of Daily Living (ADL) as assessed by Katz ADL score.
 - Time to clinical stability.
 - Improvement on the ordinal scale.
 - Rate of mortality and complications.
- The antiviral activity based on nasal RSV shedding using qRT-PCR assay (secondary for Part 1 only) and the time to cessation of nasal RSV shedding.
- The impact of ALS-008176 on the emergence of resistant strains of RSV.
- The PK of ALS-008112 and ALS-008144 (and other metabolites, if applicable) in plasma.
- The relationship between the PK and pharmacodynamics (PD; antiviral activity, clinical symptoms, and selected safety parameters) after single (LD) and repeated oral dosing (MD) of ALS-008176.

Exploratory Objectives

The exploratory objectives for Part 1 and Part 2 are to evaluate in hospitalized adults who are infected with RSV:

- The relationship between viral kinetics and clinical outcome, including the relationship between RSV RNA viral load and:
 - Oxygen supplementation.
 - Duration of hospitalization.
 - Katz ADL score.
 - Clinical stability.
- The impact of the baseline viral subtype and genotype on the antiviral activity.
- Onset of complications after initiation of treatment.

- The impact of ALS-008176 on the clinical course of RSV during and following hospitalization as assessed by the subject in the electronic Clinical Outcome Assessment (eCOA) using various scoring systems.
- The impact of RSV and its treatment on health-related quality of life (HRQoL) as assessed by the subject in the eCOA.
- The relationship between the Katz ADL score and the subject eCOA responses.
- Medical resource utilization to manage subjects.
- The comparison of the RSV RNA viral loads measured in mid-turbinate nasal swabs and endotracheal samples from intubated subjects.
- To explore the evolution of diffusing capacity of the lung for carbon monoxide (DLCO) and spirometry in subjects hospitalized with RSV infection.

Additionally, the impact of ALS-008176 on the infectious viral load may be evaluated using a quantitative culture of RSV (plaque assay) on a selected number of subjects and samples (mid-turbinate nasal swabs [if non-intubated] or mid-turbinate nasal swabs and endotracheal samples [if intubated]) at the sponsor's discretion.

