Blood sampling for pharmacokinetics ^w		X	X	X	X			X				
Biomarkers												
Blood sampling for biomarkers (host RNA)	X	X	X		X					X		
Ongoing Subject Review												
Concomitant therapy ^x	X	X	X	X	X	X	X	X	X	X	X	X
Adverse events ^y	X	X	X	X	X	X	X	X	X	X	X	X

Abbreviations: ADL: Activities of Daily Living; AE: adverse event; bid: twice daily; CPE: complete physical examination; DBP: diastolic blood pressure; DLCO: diffusing capacity of the lung for carbon monoxide; DPE: directed physical examination; ECG: electrocardiogram; eCOA: electronic Clinical Outcome Assessment; eCRF: electronic case report form; EoS: end of study; EQ-5D-5L: EuroQol 5 Dimension 5 level version; HRQoL: health-related quality of life; ICF: informed consent form; IDMC: Independent Data Monitoring Committee; LD: loading dose; MD: maintenance dose; PK: pharmacokinetic(s); Q4h: every 4 hours; Q8h: every 8 hours; RI-PRO: respiratory infection patient-reported outcome; RNA: ribonucleic acid; RSV: respiratory syncytial virus; SAE: serious adverse event; SBP: systolic blood pressure; SpO₂: peripheral capillary oxygen saturation.

Footnotes:

- a. If a subject is discontinued from study drug, a follow-up visit will be scheduled 2 days (+2 days), 5 days (+2 days), 9 days (+2 days), and 23 days (±2 days) after the last dose of study drug was administered. Assessments should be performed as indicated in the [Time and Events Schedule](#), respectively for the Day 7, Day 10, Day 14, and Day 28 visit.
- b. The subject may be discharged after the Day 2 study procedures. Subjects may also remain hospitalized if deemed appropriate by the investigator. Days 3 to 6 assessments are to be performed on a daily basis or as indicated only if the subject is still hospitalized with the exception of administration of study drug dose, mid-turbinate nasal swabs, and subject eCOA, which are to be continued at home. Hospitalization duration will not be extended solely for study purposes. Telephone calls to subjects to facilitate compliance with study procedures between outpatient study visits are permitted.
- c. If dose duration is increased to up to 10 days, then all assessments performed on Day 7 will again be performed 1 day (+2 days) after administration of the last MD.
- d. Assessments are to be performed once daily or as indicated only if the subject is still hospitalized.

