collected at home, the subject (or the subject's spouse, partner, relative, or friend) should collect swab specimens after being trained by the investigator/study-site personnel. Subjects will be required to document the actual dates and times of collection of the nasal swab at home on the electronic device used for eCOA. Nasal swabs collected at home should be stored immediately between 2°C and 8°C (in the refrigerator) and brought to the site at the next visit.

Hospitalization duration will not be extended solely for study purposes. Telephone calls to the subjects to facilitate compliance with study procedures between outpatient study visits are permitted.

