4.2.3. Primary Efficacy Endpoint

4.2.3.1. Definition

The primary estimates of the AUC will be derived from a mixed model (see section 4.2.3.2 for the detailed specification). No imputations of missing data from nasal swabs post-baseline will be done in this model, as this mixed model would allow to make inferences under the *missing at random* assumption.

Note that for the primary endpoint the following rules apply:

- Only values as provided by the central lab will be used.
- Baseline (Day 1) is defined as the last measurement before first intake. In case a result is available that is no later than 1 hour after treatment initiation this may be used but only if no pre-treatment observation is available.
- If for the baseline assessment the central laboratory value is missing, the value that will be imputed is based on the average value as based on the analysis population (ITT-i, ITT or PP population).
- For all post-baseline days the RSV RNA viral load result of the swab that was performed at that day will be used, counting from the Day of first treatment which is defined as Day 1.
- In case multiple nasal swabs were taken on a single day the average on the log scale will be used as the value for that subject.

As a sensitivity analysis, descriptive statistics will be provided for the viral load AUC calculated by the trapezoidal summation rule, based on planned days of sampling (Baseline visit up till/including Day 7 visit, or up to 11 days if the dose duration is extended to up to 10 days), including the timepoints with (imputed) values available:

$$AUC_{0-7 \text{ days}} = \frac{1}{2} \sum_{i=1}^n (y_i + y_{i-1}) \times (t_i - t_{i-1})$$

where $i=1,2,3,\dots,n$ are the time points when post baseline samples are collected, y_i is the log 10 viral load at the time and t_i is the time in hours post baseline. y_0 is the baseline log 10 viral load. t_0 is time 0.

The following additional rules, on top of the rules of the primary analysis, will be applied to deal with missing values post-baseline before calculating the Viral load AUC:

- Missing value between baseline and day 7 will be imputed by intrapolation.
- If the last observations are missing, the last available observation will be carried forward. Unscheduled assessments will be included and will be eligible for carrying forward.

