4.2.4. Secondary Efficacy Endpoints

4.2.4.1. Definition

Formulae to be used for derived variables, including data conversions, are provided in [Table 1](#). In the derivation of durations described below, no imputation of the start and/or end date/time will be performed.

Table 1. Calculations and Conversion Formulae

Measurement	Formula
Length of hospital stay (hours) [Time-to event]	(Date and time of event or censoring - date and time of first dose of study drug)/3600, rounded to one decimal
Time to readiness for discharge (hours) [Time-to-event]	Subjects who complete or withdraw from the study prior to the event will be censored at the date of completion or withdrawal. If the time is not available they will be censored at 12:00. In case of death prior to an event the time of death will be taken as censoring time (or 12:00 if not available).
Length of hospital stay since hospital admission (hours) [Time-to event]	(Date and time of event or censoring - date and time of hospital admission)/3600, rounded to one decimal
Time to readiness for discharge since hospital admission (hours) [Time-to-event]	Subjects who complete or withdraw from the study prior to the event will be censored at the date of completion or withdrawal. If the time is not available they will be censored at 12:00. In case of death prior to an event the time of death will be taken as censoring time (or 12:00 if not available).
ICU duration of stay (hours) [Duration]	sum of [(end date and time of event - start date and time of event)/3600], rounded to one decimal
Duration of supplemental oxygen (hours) [Duration] (3 separate parameters: supplemental oxygen, invasive ventilator, non-invasive ventilator)	If the end date is missing, the end date is considered to be after study completion or withdrawal. If the initial start time is prior to the first dose of study drug, the duration prior to the first dose of study drug will be deducted from the overall duration.
Need for feeding, hydration by IV catheter/enteral tube (hours) [Duration] (2 separate parameters)	If the end date and time is after the study completion/discontinuation, the duration after the date and time of study completion/discontinuation will be deducted from the overall duration. If the time is not available it will be put at 12:00.
Time to end of Oxygen supplementation (hours)	(Date and time of event or censoring - date and time of first dose of

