4.6. OTHERS

Relationship between RSV RNA viral load and RSV viral load by qRT-PCR (intubated subjects)

To make a comparison of the RSV RNA viral loads measured in mid-turbinate nasal swabs and endotracheal samples from intubated subjects, scatter plots will be created plotting the RSV RNA viral loads versus the RSV viral load as measured by qRT-PCR of endotracheal samples.

Relationship between viral kinetics and clinical outcome

Kaplan-Meier analysis by quartiles of viral load $AUC_{0-7 \text{ days}}$ for:

- The Length of Hospital Stay/Need (both since treatment initiation and since hospital admission)
- Time to return to pre-RSV functional status (KATZ ADL score)
- Time to clinical stability

A summary table including number of subjects included in the analysis, number of subjects censored, 25th and 75th percentiles and median with 95% confidence intervals based on log-log transformation method, will be presented by quartiles of viral load $AUC_{0-7 \text{ days}}$ parameter.

A Tabulation of the need for additional oxygen supplementation will be presented by quartiles of viral load $AUC_{0-7 \text{ days}}$.

Evolution of diffusing capacity

To explore the evolution of diffusing capacity of the lung for carbon monoxide (DLCO) and spirometry in subjects hospitalized due to RSV infection, descriptive statistics and mean (SE) plots will be shown and the changes from baseline calculated by treatment group.

Impact of ALS-008176 on the infectious viral load

The impact of ALS-008176 on the infectious viral load will be evaluated by descriptive statistics on the RSV infectious viral load as measured using quantitative viral culture (plaque assay).

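### The AUC0-7 quartile curves in SAP 4.6 classify subjects partly on viral loads from after their event, so they cannot show whether viral load predicts clinical outcome

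*Protocol*

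**What the plan says.** Protocol 2.1.1 lists as exploratory "The relationship between viral kinetics and clinical outcome, including the relationship between RSV RNA viral load and" oxygen supplementation, duration of hospitalization, Katz ADL score and clinical stability.

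SAP 4.6 implements this as "Kaplan-Meier analysis by quartiles of viral load" AUC0-7 for three outcomes: hospital stay/need, return to pre-RSV Katz status, and clinical stability. It adds a summary table of counts, percentiles and medians, and a tabulation of additional oxygen need by the same quartiles. No landmark, restriction to subjects still at risk, time-updated viral load or covariate adjustment is named.

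The timing rules are elsewhere:

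- **AUC window.** SAP 4.2.3.1 builds the trapezoidal AUC from baseline through the Day 7 visit, which SAP 2.1 windows as Days 7 to 9. Gaps inside the window are interpolated. For gaps at the end, "If the last observations are missing, the last available observation will be carried forward".
- **Clocks.** SAP Table 1 (4.2.4.1) measures all these times from first dose. Hospital stay and readiness for discharge are also measured from admission.
- **Discharge.** Time and Events Schedule, footnote b: "The subject may be discharged after the Day 2 study procedures".
- **Swabs after discharge.** They continue daily. Under footnote s, trained staff take them wherever possible; otherwise the trained subject or a relative does. Protocol 9.1.3 says home swabs "should be stored immediately between 2°C and 8°C (in the refrigerator) and brought to the site at the next visit". Under Protocol 9.1.4, Day 7 is an outpatient visit for discharged subjects.

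**The concern.** The grouping variable is not complete until Day 7, but follow-up for the outcome starts at first dose or earlier. For someone discharged on Day 3, the later loads that help fix the quartile come after the outcome. Discharge can also alter those loads. It may move Day 3 to 6 sampling from staff to the subject, and a Day 3 home swab could be refrigerated for 4 days (Day 7 minus Day 3) to 6 days (Day 9 minus Day 3). If late swabs are missing, the last in-hospital value stands in for them. A subject who dies is censored at death for hospital stay but is ranked on values carried past it.

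At stake is the reading of one exploratory output. A gradient across quartiles could mean that viral load drives recovery, that recovery changes how viral load is recorded, or both.

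**Working it through.** The plan states no figure for this analysis, so there is nothing to reproduce. Two checks follow.

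**1. How many subjects could be affected**

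Inputs: Day 1 to Day 7 is 6 days (SAP 4.2.3.1). Time to event is assumed exponential with median M days, because the documents give no expected time.

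- Share with the event before the Day 7 swab: 1 − 2^(−6/M).
- Mean share of the AUC window lying after the event: 1 − (1 − e^(−6λ))/(6λ), with λ = ln 2/M.

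| Assumed median M (days) | Event before Day 7 swab | Mean share of window after event |
|---|---|---|
| 2 | 88% | 58% |
| 4 | 65% | 38% |
| 6 | 50% | 28% |
| 8 | 41% | 22% |
| 10 | 34% | 18% |

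For example, M = 6 gives 1 − 2^(−1) = 50%.

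**2. What post-event values can do to the curves**

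Simulation with no true link between viral load and discharge: 90 subjects, 500 runs, median discharge 5 days (1-day minimum). Assumed viral-load parameters are baseline mean 6 log10 (SD 1.5), decline 0.5 log10 per day (SD 0.2) and residual SD 0.7. Subjects are grouped by quartile of trapezoidal AUC0-7. The last column is the rejection rate of a 5% Spearman test. The SAP plans no such test; the rate serves only as a gauge.

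| Post-discharge swabs | Median discharge, lowest v highest quartile (days) | Rejection |
|---|---|---|
| Unaffected | 5.2 v 5.2 | 6% |
| All read 0.5 log10 lower | 4.6 v 5.6 | 10% |
| All read 1.0 log10 lower | 4.1 v 6.2 | 34% |
| All missing, carried forward | 6.2 v 3.8 | 50% |

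The last three rows are upper bounds. Rows 2 and 3 count the Day 7 swab as home-collected, although it is due at a clinic visit. Row 4 requires the Day 7 swab to be missing too, since otherwise earlier gaps are interpolated.

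The effect of realistic collection was checked with a lognormal stay (median 96 h, sigma 0.7; 1,500 runs) and a 5% Kruskal-Wallis test, also not planned in the SAP. Rejection for home swabs lower by 0.3, 0.5 and 1.0 log10 (assumed shifts) was:

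- all post-discharge swabs at home: 6%, 9%, 20%;
- Day 7 at clinic: 6%, 7%, 15%;
- Day 7 at clinic and half of the rest taken by staff: 4%, 5%, 8%.

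**The case against.** The strongest reply is that the plan promises only a description of a relationship. Protocol 2.1.1 does not mention prediction, SAP 4.6 attaches no test, and AUC to Day 7 is the primary virological measure, so tabulating outcome against it is coherent. This stands. A reader might infer that the curves are meant to validate AUC as the primary endpoint; no passage says so.

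A reader might also infer that the grouping is biased by construction, as in immortal-time bias. For discharge this is not supported: swabbing continues afterwards, and with unaffected post-event loads the curves coincide. Distortion needs a collection or missing-data effect. The documents give neither size nor direction for a home-swab effect, and home collection is a fallback for Days 3 to 6 only. Nor does the distortion necessarily favour a link between low load and early discharge, because carry-forward pushes the other way.

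Time-ordered analyses exist in part. SAP 4.2.5.5.1 correlates viral load with the normalized Katz score for every pair of days, explicitly to look for delayed relationships. The accelerated failure time models in SAP 4.2.4.2 relate baseline load to hospital stay and clinical stability, with treatment in the model and symptom duration as a candidate covariate. The first largely answers the point for Katz. The second concerns baseline load, not viral kinetics on treatment. For hospital stay, clinical stability and oxygen need, no planned analysis relates on-treatment load to later outcome in time order.

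**Conclusion.** The point holds as a minor one. Subjects whose event precedes the Day 7 visit are grouped partly on post-event values: 88% to 34% of them for assumed medians of 2 to 10 days. Any resulting distortion could run in either direction, and its size rests on assumptions the documents cannot settle. With mostly staff-collected swabs and few missing values it may be negligible. Even then, the curves cannot separate prediction from consequence. The objective itself is sound; the weakness is in SAP 4.6. The primary analysis and all treatment comparisons are unaffected.

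**What to change.** In SAP 4.6, for hospital stay/need and clinical stability (and Katz return if wanted), add one time-ordered analysis as the basis for interpretation:

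- a Cox model with time-updated log10 viral load; or
- a Day 3 landmark: classify subjects on baseline-to-Day 3 viral load, include only those still event-free, and restart the clock at Day 3.

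Include treatment arm, baseline log10 load and days since symptom onset in either. Keep the AUC0-7 quartile curves as descriptive output, with a footnote that the grouping uses values from after the event. The oxygen tabulation by the same quartiles could carry the same footnote.

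The cost is SAP wording and one re-programmed exploratory output; the daily swabs are already scheduled. The landmark also loses subjects. If median stay is 96 h, discharge by 48 h is Φ(ln 0.5/0.7) = 16% under a lognormal with sigma 0.7, or 1 − 2^(−48/96) = 29% under an exponential. The loss may be larger for clinical stability and Katz, where SAP Table 1 allows times of 0. Report the number excluded. The time-updated model avoids most of this loss. The landmark also asks a narrower question than AUC0-7, about early viral decline, which is a reason to keep the descriptive curves beside it.
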